### Objectives:

1. To determine the efficacy of PCI as a treatment for coronary artery disease in HFpEF.
2. To examine the mechanistic relationship between ischaemia and symptoms, and how changes in these relate following PCI, in patients with HFpEF and coronary artery disease.
3. To demonstrate the feasibility of a multicentre, placebo procedure controlled randomised trial of PCI in patients with HFpEF and coronary artery disease.
4. To co-produce this trial with patient representatives, to ensure it effectively addresses their needs and priorities.
5. To enrol an inclusive group of participants, ensuring representation of the population of those with HFpEF and coronary artery disease and that all individuals have the same opportunity of participation following the principles of equality, diversity and inclusion.
6. To create new, generalisable learning as to how diversity in interventional heart failure trials can be improved.
7. To inform the feasibility and design of a phase-III randomised controlled trial of clinical and cost effectiveness, should this study suggest efficacy.

## 5 STUDY DESIGN & FLOWCHART

### 5.1 Study Design

**Research design:** a phase II, multi-centre, randomised, double-blind, placebo procedure-controlled superiority trial comparing PCI to a placebo procedure in patients with HFpEF and coronary artery disease.

**Randomisation:** Patients with HFpEF and coronary artery disease will be randomised in a 1 to 1 manner to either PCI or placebo procedure using an online randomisation system in permuted blocks of varying size. Randomisation will be stratified by recruiting site.

#### Outcome measures:

- **Primary efficacy:** The primary efficacy outcome is the difference in KCCQ-OSS between treatment groups at 6-month follow-up. The Kansas City Cardiomyopathy Questionnaire (KCCQ) is the most widely used disease-specific tool for patient reported quality of life outcomes in heart failure, has been specifically validated in HFpEF and is the recommended tool for assessing functional and psychosocial outcomes in the International Consortium for Health Outcomes Measurement (ICHOM) standard outcome set for heart failure published in 2020.
- **Primary mechanistic:** The primary mechanistic outcome is the difference in CFR between treatment groups, after PCI has been performed in the PCI group. CFR is an independent predictor of future adverse cardiovascular events and allows us to determine the relationship between the severity of epicardial and microvascular disease and quality of life.
- **Secondary outcomes:** Key secondary outcomes include all-cause death and hospitalisation for heart failure. Further secondary outcomes include the efficacy of blinding (assessed using standard tools), the ICHOM standard outcome set for heart failure, individual components of the KCCQ (including total symptom score and clinical summary score), New York Heart Association (NYHA) functional class, difference in NT-pro-BNP at six months and difference in left ventricular ejection fraction (LVEF) and diastolic function (mitral E/e') at six months.
- **Secondary mechanistic:** Secondary mechanistic outcomes include change in invasively measured FFR, CFR and microvascular resistance from pre- to post-PCI in all target coronary arteries measured during the PCI procedure.

## 5.2 Outcome definitions

The following serious adverse events will be collected as secondary outcomes and are expected to occur during this study, and will not require additional reporting as SAEs (see section 7 below). Where possible, definitions are aligned with the ARC-2 consensus document.

Outcome	Endpoint definition
Death	
Death from all-causes can be defined as one of the following classifications:
 
 
Cardiovascular death Defined as any death resulting from cardiovascular causes. This may include death caused by: 
 
a. Acute MI
 
b. Sudden cardiac, including unwitnessed death
 
c. Heart Failure
 
d. Stroke
 
e. Cardiovascular procedures
 
f. Cardiovascular haemorrhage
 
g. Other cardiovascular cause
 
 
 
Non-cardiovascular death Defined as any death not thought to be the result of a cardiovascular cause. This may include death caused by: 
 
a. Malignancy
 
b. Pulmonary causes
 
c. Infection (including sepsis)
 
d. Gastrointestinal causes
 
e. Accident or trauma
 
f. Other non-cardiovascular organ failure
 
g. Other non-cardiovascular cause
 
 
 
Undetermined Defined as death not classified under any other category because of the absence of any relevant source documents. For endpoint determination these deaths will be classified as cardiovascular.
 

Myocardial infarction	
Myocardial infarction will be defined according to the ARC-2 definition below.
 
 
Spontaneous myocardial infarction (prior to or ≥48 hours after PCI/CABG)  Detection of a rise and/or fall of cardiac troponin I or T, with at least one value higher than the 99th percentile upper reference limit (URL) AND symptoms consistent with ischaemia OR dynamic electrocardiogram (ECG) changes (including ≥1mm ST elevation or ST depression, new left bundle branch block (LBBB) or >3mm T-wave
 

	
inversion OR imaging evidence of new loss of viable myocardium or new regional wall motion abnormality in a pattern consistent with an ischaemic aetiology.
 
2. Periprocedural MI (within 48 hours after PCI/CABG) including index procedure and subsequent unplanned revascularisation
 
Absolute rise in cardiac troponin I or T (from baseline) <math>\geq 35</math> times the URL AND new significant Q-waves or equivalent OR flow-limiting angiographic complications OR new "substantial" loss of myocardium on imaging.
 
Flow-limiting angiographic complications are defined as loss of patency of a major vessel, graft or side branch, embolization, disruption of collateral flow, persistent slow flow or no reflow, major dissection, angiographic new occlusion or flow limiting stenosis in a coronary artery bypass graft or native coronary artery occlusion.
 
3. Significant periprocedural myocardial injury (within 48 hours after PCI/CABG) including index procedure and subsequent unplanned revascularisation
 
Absolute rise in cardiac troponin I or T (from baseline) <math>\geq 70</math> times the URL.

Stroke	
Stroke will be defined using NeuroARC definitions as one of the following classifications:
 
Type 1: Overt Central Nervous System (CNS) injury – Acutely symptomatic brain or spinal cord injury
 
 
Type 1a Ischaemic stroke Sudden onset of neurological signs or symptoms fitting with a focal or multifocal vascular territory within the brain, spinal cord or retina that persist for <math>\geq 24</math> hours or until death, with pathology or neuroimaging that demonstrates either CNS infarction in the corresponding territory (with or without haemorrhage) OR absence of other apparent causes (including haemorrhage), even if no evidence of acute ischaemia in the corresponding vascular territory is detected.
 
 
OR
 
Symptoms lasting <math><24</math> hours with pathology or neuroimaging confirmation of CNS infarction in the corresponding vascular territory.
 
 
Subtype 1aH Ischaemic stroke with haemorrhagic conversions Ischaemic stroke includes haemorrhagic conversions. These should be subclassified as Class A or B when conversion ischemic stroke is the
 

	
primary mechanism and pathology or neuroimaging confirms a haemorrhagic conversion.
 
Class A: Petechial haemorrhage: Petechiae or confluent petechiae within the infarction or its margins, but without a space-occupying effect.
 
Class B: Confluent haemorrhage: Confluent haemorrhage or hematoma originating from within the infarcted area with space-occupying effect.
 
 
 Type 1b Symptomatic intracerebral haemorrhage  Rapidly developing neurological signs or symptoms (focal or global) caused by an intraparenchymal, intraventricular, spinal cord, or retinal collection of blood, not caused by trauma. 
 
 Type 1c Symptomatic subarachnoid haemorrhage  Rapidly developing neurological signs or symptoms (focal or global) and/or headache caused by bleeding into the subarachnoid space, not caused by trauma. 
 
 Type 1d Stroke not otherwise specified  An episode of acute focal neurological signs or symptoms and/or headache presumed to be caused by CNS ischemia or CNS haemorrhage, persisting <math>\geq 24</math> h or until death, but without sufficient evidence to be classified (i.e., no neuroimaging performed). 
 
 Type 1e Symptomatic hypoxic-ischaemic injury  Non-focal (global) neurological signs or symptoms due to diffuse brain, spinal cord, or retinal cell death (confirmed by pathology or neuroimaging) in a nonvascular distribution, attributable to hypotension and/or hypoxia. 
 
 
Type 2: Covert CNS injury – Acutely asymptomatic brain or spinal cord injury
 
 
 Type 2a Covert infarction  Brain, spinal cord, or retinal cell death attributable to focal or multifocal ischemia, based on neuroimaging or pathological evidence of CNS infarction, without a history of acute neurological symptoms consistent with the lesion location. 
 
 Subtype 2aH Covert infarction with haemorrhagic conversions  Covert CNS infarction includes haemorrhagic conversions. These should be subclassified as Class A or B when CNS infarction is the primary mechanism and neuroimaging or pathology confirms a haemorrhagic conversion. 
 

--	---

	
Class A: Petechial haemorrhage petechiae or confluent petechiae within the infarction or its margins, but without a space-occupying effect.
 
Class B: Confluent haemorrhage: confluent haemorrhage originating from within the infarcted area with a space-occupying effect.
 
 
• Type 2b Covert haemorrhage Neuroimaging or pathological evidence of CNS haemorrhage within the brain parenchyma, subarachnoid space, ventricular system, spinal cord, or retina on neuroimaging that is not caused by trauma, without a history of acute neurological symptoms consistent with the bleeding location.
 
 
Type 3: Neurological dysfunction – Acutely symptomatic without brain or spinal cord injury
 
 
• Type 3a Transient ischemic attack (TIA) Transient focal neurological signs or symptoms (lasting <24 h) presumed to be due to focal brain, spinal cord, or retinal ischemia, but without evidence of acute infarction by neuroimaging or pathology (or in the absence of imaging).
 
• Type 3b Delirium without CNS injury Transient non-focal (global) neurological signs or symptoms (variable duration) without evidence of cell death by neuroimaging or pathology.
 

Hospitalisation	
Hospitalisation will be defined by the Heart Failure Academic Research Consortium (HF-ARC) consensus document.
 
Hospitalisation is defined as any hospital or virtual ward admission where length of stay is <math>\geq 24</math> hours, and will be classified as one of the following:
 
 
1. Cardiovascular hospitalisation Admission with a defined cardiovascular cause. This may include but are not limited to acute MI, arrhythmia or conduction system disturbance, cardiogenic shock, cardiovascular device failure, cardiovascular haemorrhage including tamponade, cardiovascular infection, cardiovascular procedure-related, HF (including both left and right ventricular dysfunction), peripheral arterial disease, thromboembolism, stroke, and sudden cardiac death.
 
2. Heart failure hospitalisation Admission with a primary diagnosis of heart failure.
 
3. Non-cardiovascular hospitalisation Admission with a defined non-cardiovascular cause. This may include but are not limited to gastrointestinal disorders including haemorrhage, hepatic failure, malignancies, mental deterioration not due to cerebrovascular disease, non-cardiovascular infections
 

[figure not shown]
	
and sepsis, renal failure, orthopaedic injuries, pulmonary disease, respiratory failure, attempted suicide, and trauma.
 
4. Hospitalisation due to unknown or undefined cause Admission where there is identified primary cause or where the primary cause cannot be determined.
 
5. Elective hospitalisation Admission for elective diagnostic or therapeutic procedures.

Atrial fibrillation	
New-onset AF is defined as a new onset or a first detectable episode of AF, whether symptomatic or not, and will be classified as one of the following categories:
 
1. Permanent or persistent This includes persistent (lasts longer than 7 days), longstanding persistent (duration at least 12 months) or permanent (no further attempts to restore or maintain sinus rhythm).
 
2. Paroxysmal Episodes terminate within 7 days of onset.

Bleeding	
Bleeding will be defined using the Bleeding Academic Research Consortium (BARC) 3 criteria as below:
 
Type 0: No bleeding
 
Type 1
 
 
Bleeding that is not actionable and does not cause the patient to seek unscheduled performance of studies, hospitalization, or treatment by a healthcare professional; may include episodes leading to self-discontinuation of medical therapy by the patient without consulting a healthcare professional
 
 
Type 2
 
 
Any overt, actionable sign of haemorrhage (e.g. more bleeding than would be expected for a clinical circumstance, including bleeding found by imaging alone) that does not fit the criteria for type 3, 4, or 5 but does meet at least one of the following criteria: (1) requiring nonsurgical, medical intervention by a healthcare professional, (2) leading to hospitalization or increased level of care, or (3) prompting evaluation
 
 
Type 3
 
 
Type 3a
 

	
 
○ Overt bleeding plus haemoglobin drop of 3 to <5 g/L* (provided haemoglobin drop is related to bleed)
 
○ Any transfusion with overt bleeding
 
• Type 3b 
 
○ Overt bleeding plus haemoglobin drop <math>\geq 5</math> g/dL* (provided haemoglobin drop is related to bleed)
 
○ Cardiac tamponade
 
○ Bleeding requiring surgical intervention for control (excluding dental/nasal/skin/haemorrhoid)
 
○ Bleeding requiring intravenous vasoactive agents
 
 
 
• Type 3c 
 
○ Intracranial haemorrhage (does not include microbleeds or haemorrhagic transformation, does include intraspinal)
 
○ Subcategories confirmed by autopsy or imaging or lumbar puncture
 
○ Intraocular bleed compromising vision
 
 
 
 
Type 4: CABG-related bleeding
 
 
• Perioperative intracranial bleeding within 48 hours
 
• Reoperation after closure of sternotomy for the purpose of controlling bleeding
 
• Transfusion of <math>\geq 5</math> units whole blood or packed red blood cells within a 48-hour period
 
• Chest tube output <math>\geq 2</math>L within a 24-hour period
 
 
Type 5: fatal bleeding
 
 
• Type 5a 
 
○ Probable fatal bleeding; no autopsy or imaging confirmation but clinically suspicious
 
 
 
• Type 5b 
 
○ Definite fatal bleeding; overt bleeding or autopsy or imaging confirmation
 
 
 

Vascular complication	
Vascular complications will be defined according to the Valve Academic Research Consortium 2 (VARC-2) criteria as below:
 
Major complication
 
 
• Aortic dissection or aortic rupture, annulus rupture, left ventricle perforation, or new apical aneurysm/pseudo-aneurysm OR
 
• Access site or access-related vascular injury (dissection, stenosis, perforation, rupture, arterio-venous fistula, pseudoaneurysm, haematoma, irreversible nerve injury, compartment syndrome, percutaneous closure device failure) leading to death, life-threatening or major (VARC) bleeding, visceral ischaemia, or neurologic impairment OR
 

	
 
• Distal embolisation (non-cerebral) from a vascular source requiring surgery or resulting in death, amputation, limb or visceral ischaemia, or irreversible end-organ damage OR
 
• Unplanned endovascular or surgical intervention resulting in death, major (VARC) bleeding, visceral ischaemia, or neurologic impairment OR
 
• New ipsilateral lower extremity ischaemia documented by patient symptoms, physical exam, and/or decreased or absent blood flow on lower extremity angiogram
 
• Surgery for access site-related nerve injury OR
 
• Permanent access site-related nerve injury
 
 
Minor complication
 
 
• Access site or access-related vascular injury (dissection, stenosis, perforation, rupture, arterio-venous fistula, pseudoaneurysm, haematomas, percutaneous closure device failure) not leading to death, life-threatening or major (VARC) bleeding, visceral ischaemia, or neurological impairment OR
 
• Distal embolisation treated with embolectomy and/or thrombectomy and not resulting in amputation or irreversible end-organ damage OR
 
• Unplanned endovascular stenting or unplanned surgical intervention not meeting the criteria for a major vascular complication OR
 
• Vascular repair or the need for vascular repair (via surgery, ultrasound-guided compression, transcatheter embolisation, or stent-graft)
 
 
Percutaneous closure device failure
 
 
• Failure of a closure device to achieve haemostasis at the arteriotomy site leading to alternative treatment (other than manual compression or adjunctive endovascular ballooning)
 

Acute renal failure	
Acute kidney injury is defined according to the Acute Kidney Injury Network (AKIN) criteria as any of the following:
 
 
1. Increase in serum creatinine <math>\geq 0.3</math> mg/dL (<math>\geq 26.5</math> <math>\mu</math>mol/L) within 48 hours; or
 
2. Increase in serum creatinine <math>\geq 1.5</math> times baseline, which is known or presumed to have occurred within the prior 7 days; or
 
3. Urine volume <math>< 0.5</math> mL/kg/h for 6 hours.
 


Repeat revascularisation
	
Repeat revascularisation will be defined according to the ARC-2 criteria as one of the following classifications:
 
 
1. Target lesion Defined as the treated segment including the 5-mm margin proximal and distal to the stent/scaffold
 
2. Target lesion revascularisation Target lesion revascularisation is defined as a repeat percutaneous intervention of the target lesion or bypass surgery of the target vessel performed for restenosis or other complication of the target lesion.
 
3. Target vessel The target vessel is defined as the entire major intervened coronary vessel including side branches.
 
4. Target vessel revascularisation Target vessel revascularisation is defined as any repeat percutaneous intervention or surgical bypass of any segment of the target vessel including the target lesion.
 
5. Target vessel non-target lesion revascularisation Target vessel nontarget lesion revascularisation is defined as any repeat percutaneous intervention or surgical bypass of the target vessel for pre-existing disease, disease progression or other reasons unrelated to the target lesion as defined above.
 

---------------------------------	---

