## 9 ASSESSMENT OF SAFETY

### 9.1 Definition

**Unexpected** events that have not been defined as an outcome (see section 5.2) should be reported as either a serious adverse event (SAE) or non-serious adverse event (NSAE) depending on their severity.

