#### 9.4.2 Assessment of Causality

Probable: A causal relationship is clinically / biologically highly plausible and there is a plausible time sequence between onset of the adverse event and the PCI procedure.

Possible: A causal relationship is clinically / biologically plausible and there is a plausible time sequence between onset of the adverse event and the PCI procedure.

Unlikely: A causal relationship is improbable, and another documented cause of the adverse event is most plausible.

Unrelated: A causal relationship can definitely be excluded and another documented cause of the adverse event is most plausible.

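### Listed outcomes, including every death and every admission of 24 hours or more, are exempt from SAE reporting even when a trial procedure, sedation or study tablet is the suspected cause, and the causality scale names only the PCI procedure

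*Protocol*

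**What the plan says.** Section 5.2 introduces its outcome table by saying that the listed serious events "are expected to occur during this study, and will not require additional reporting as SAEs". It sends the reader to section 7 for the reporting rules, but section 7 is Laboratories; safety reporting is section 9.

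The table is broad:
- **Death:** "Death from all-causes can be defined as one of the following classifications". The classes are cardiovascular (deaths from cardiovascular procedures are named), non-cardiovascular ("Defined as any death not thought to be the result of a cardiovascular cause") and undetermined.
- **Admission:** "Hospitalisation is defined as any hospital or virtual ward admission where length of stay is" 24 hours or more. Its five categories are cardiovascular, heart failure, non-cardiovascular, unknown cause and elective.
- **Other entries:** these include bleeding, vascular complications, periprocedural MI, acute kidney injury, and stroke, which has a subtype for hypoxic-ischaemic injury.

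Section 9.1 applies the exemption: only unexpected "events that have not been defined as an outcome (see section 5.2) should be reported as either a serious adverse event" or a non-serious one. Section 9.2 counts death and in-patient hospitalisation among its SAE criteria. It requires unexpected SAEs to reach the CTU within 7 days, with a causality assessment by the site PI. In section 9.4.2, 'Probable' and 'Possible' both require that "there is a plausible time sequence between onset of the adverse event and the PCI procedure". Section 9.5 notifies Sponsor, REC and DMC only of SAEs that are both unexpected and rated probable or possible.

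**The concern.** Exempting endpoints from SAE reporting is ordinary practice where the events are expected from the disease. Such an exemption normally stops at events thought to be caused by the trial itself, and this one does not. Every participant has invasive angiography and physiology with benzodiazepine and opiate sedation (6.5.2). Half then have a placebo procedure without a stent (6.5.4.2), and all receive clopidogrel or matching placebo for up to 6 months (6.6). Several foreseeable serious harms of these exposures are on the exempt list.

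At stake is prompt, individual review of a death or serious admission that the trial may have caused. For events that do enter section 9, the rating that decides onward notice is tied to one procedure, which only one arm is allocated to receive.

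**Working it through.** No arithmetic applies: the point does not depend on alpha, power, effect size or event counts, and the protocol gives no figure to reproduce. The check follows two serious events through the text.

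**Event A: a death, or an admission of 24 hours or more, suspected to be caused by PCI, the placebo procedure, sedation or a study tablet.**
1. *Is it a listed outcome (5.2)?* Yes. Deaths of every cause are covered, and the admission categories include the residual one, "Admission where there is identified primary cause or where the primary cause cannot be determined". No wording removes events suspected to be trial-related.
2. *Does it enter SAE reporting (9.1)?* No, because it is defined as an outcome. This is so although section 9.2 uses death and in-patient hospitalisation to define an SAE.
3. *Is it reported to the CTU within 7 days and rated for causality (9.2, 9.4.2)?* No. Both apply only to events that pass step 2.
4. *Can it meet the notice condition (9.5)?* No. The condition needs an unexpected SAE rated probable or possible. This event is expected by declaration and has no rating.
5. *Does Appendix 4 help?* No. Its 24-hour report to the Sponsor and 15-day report to the REC are for SAEs that are related and unexpected.

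The same trace holds for listed bleeding, an obvious harm of an antiplatelet tablet: "Bleeding will be defined using the Bleeding Academic Research Consortium (BARC) 3 criteria as below". It also holds for harm from PCI itself, so the gap is not confined to the placebo arm.

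**Event B: a serious event outside the list, for example a life-threatening reaction with a stay under 24 hours.**
1. It enters section 9 and goes to the CTU within 7 days.
2. Onward notice depends on a rating of probable or possible, and both refer to the PCI procedure.
3. *Placebo procedure:* ambiguous. Section 6.12 lists the PCI procedure and the placebo procedure as separate rows. Yet 6.6 has placebo tablets taken following PCI, 6.10.2 calls everyone's visit the PCI procedure visit, and 13.1 refers to the PCI admission for all participants.
4. *Study tablets:* not covered on any reading.
5. *Rater:* section 9.2 says the site PI, but each site has two (6.8.1). The unblinded PI has no further part in care or follow-up outside emergency unblinding (6.8.3), and the blinded PI supervises follow-up (6.11). If 'PCI' is read literally, the blinded PI must rate against a procedure that they cannot know took place.

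**The case against.** The strongest reply is that the exemption is openly stated, is applied consistently in 5.2, 9.1 and 9.5, and leaves other safeguards in place. Much of this stands, and it rules out four stronger readings that a reader might infer.

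- *That an early death would first surface at the 3-month visit.* Not supported. Section 13.1 has data collected when the team learns of adverse events, and 6.10.3 and 6.12 record procedural complications and adverse events at discharge. What is missing for listed outcomes is a 7-day deadline and a causality rating.
- *That no expedited path exists at all.* Too strong. Section 9.2 makes the Chief Investigator responsible for promptly notifying findings that may harm patients, and Appendix 4 requires immediate notice of urgent safety measures. Listed outcomes can also reach the DMC in its reports; the one-year gap in 10.4 is a maximum, not a schedule. But the first two routes depend on judgement and on the Chief Investigator hearing of the event, and the third is periodic. None is a routine case-level report.
- *That the SAE route is left almost empty.* Not supported. Life-threatening events that are not listed outcomes, disability, and in-patient stays under 24 hours still qualify under 9.2.
- *That no placebo participant can be rated for causality.* Not established. Because 'PCI' is used loosely for the index procedure in both arms, a blinded PI might well rate against that procedure. The wording is ambiguous rather than prohibitive.

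The reply does not answer the missing exception for suspected relatedness, or the absence of the study tablets from the scale.

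**Conclusion.** The point holds. As written, a listed outcome suspected to be caused by a trial procedure, sedation or the study tablets has no section 9 causality rating, no 7-day CTU report and no way to trigger section 9.5 notice. This affects both arms and includes the gravest classes, deaths and admissions of 24 hours or more. For serious events outside the list, the gap is narrower: an ambiguous causality reference for the placebo procedure and none for the tablets.

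The size is given by the classes of event affected; the protocol supports no count or delay. The conclusion assumes that sites follow the text literally, and that the Appendix 3 flow diagram (not readable in the copy reviewed), the DMC charter and the working practice documents (not seen) add no exception for related events. If one of them does, the protocol text should still be brought into line with it. The point is about reporting rules only and implies nothing about clinical care.

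**What to change.** 1. **Sections 5.2 and 9.1:** keep the exemption only for listed events not judged possibly or probably related to the trial procedure, sedation or study tablets. State that related ones follow 9.2 and 9.5 even though the event type is listed as expected; without that sentence the 'unexpected' condition in 9.5 would still block them.
2. **Section 9.4.2:** replace 'the PCI procedure' with 'the trial procedure in either arm (PCI or placebo, including angiography, physiology and sedation) or the study tablets'. A blinded PI can then rate causality without knowing the allocation.
3. **Section 5.2:** correct the cross-reference from section 7 to section 9.

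The cost is a wording amendment to three sections and a few more expedited forms. Outcome definitions, data collection and the exemption for unrelated endpoints are unchanged.

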### ***Percutaneous coronary intervention***

Percutaneous coronary intervention (PCI), also referred to as coronary angioplasty and stenting, is an established treatment for coronary artery disease when the patient presents with limiting angina despite optimal pharmacological therapy or an acute myocardial infarction. Coronary patency is restored by balloon dilatation of significant coronary stenoses, followed by placement of a stent which enhances patency in the long term. The procedure is minimally invasive and associated with an in-hospital mortality of 0.14% and risk of myocardial infarction or stroke of 0.3%. The cost of elective PCI in the NHS is modest compared to many other interventions (with an average tariff cost of £1782 for an elective procedure in 2019/20). Despite the causal association and mechanistic link between coronary artery disease and HFpEF, no randomised study has assessed the efficacy or mechanistic benefits of PCI in this population.

PCI is an attractive option to improve quality of life in patients with HFpEF and coronary artery disease. Treatment with PCI has been shown to improve myocardial perfusion and attenuate the development of systolic and diastolic dysfunction during exertion. Long-term improvement in the ischaemic substrate may also reduce the development of myocardial fibrosis and progression to left ventricular systolic dysfunction which has been recognised in this population over longitudinal follow-up. Furthermore, there are concerns that many first-line drugs traditionally used to treat ischaemia may worsen symptoms in patients with HFpEF. The use of beta blockers in HFpEF is associated with chronotropic incompetence, impaired exercise capacity and higher levels of natriuretic peptide, whilst chronic use of nitrates is associated with worsening endothelial function and reduced exercise capacity in this population. A treatment which avoids these drug side effects whilst ameliorating ischaemia may therefore be beneficial. Factors which might attenuate the benefit of PCI include the high prevalence of coronary microvascular dysfunction in HFpEF which may leave a (lessened) ischaemic substrate after treatment and the extent of pre-existing cardiac remodelling which may not be reversible, as well as the systemic nature of the condition.

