### **6.5.2 On the day of the intervention**

On the day of the trial intervention, ongoing consent for the study will be confirmed and clinical consent for the invasive procedure obtained by the unblinded PI. Procedures will be performed by either the unblinded PI or an unblinded sub-investigator. Participants will receive pre-treatment with antiplatelet medication (aspirin 300mg and clopidogrel 300-600mg per local protocol). The KCCQ will be repeated to measure early changes in quality of life with medical optimisation.

Coronary angiography will be performed using standard procedure, preferentially via radial access. Following coronary angiography, a detailed physiological assessment will be performed in all target coronary arteries, including measures of fractional flow reserve (FFR), coronary flow reserve (CFR) and microvascular function. Left ventricular end diastolic pressure will be measured at rest and during handgrip exercise.

Before randomisation, patients will receive headphones playing music to ensure auditory isolation, and patients will be sedated using incremental doses of benzodiazepines and opiates to a deep level of conscious sedation.

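### Section 5.2 defines Stroke as any listed NeuroARC class, so covert lesions, TIA and delirium without CNS injury count as strokes as written

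*Protocol*

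**What the plan says.** The table in Protocol section 5.2 lists events collected as secondary outcomes. Its Stroke row opens: "Stroke will be defined using NeuroARC definitions as one of the following classifications". The classes that follow are:

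- Type 1, overt CNS injury (1a to 1e);
- Type 2, injury without acute symptoms, for example "Type 2a Covert infarction";
- "Type 3: Neurological dysfunction – Acutely symptomatic without brain or spinal cord injury", which contains TIA (3a) and "Type 3b Delirium without CNS injury".

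The criterion for Type 3b is "Transient non-focal (global) neurological signs or symptoms (variable duration) without evidence of cell death by neuroimaging or pathology". It sets no minimum duration and makes no exception for drug effects. No sentence in the row restricts the outcome to Type 1.

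Two other places bear on the point. Section 6.5.2 says that, before randomisation, "patients will be sedated using incremental doses of benzodiazepines and opiates to a deep level of conscious sedation", so both arms are exposed. The Introduction, under Percutaneous coronary intervention, gives the only related rate in the document, a "risk of myocardial infarction or stroke of 0.3" per cent.

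**The concern.** The row counts as stroke some events that its own Type 3 heading describes as involving no CNS injury. A site or analyst who follows the text as written would add TIA, delirium and any incidental covert lesion to the stroke count.

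Stroke is a safety outcome in a trial that compares an invasive procedure with a placebo procedure. An inflated count misstates the risk shown to the Data Monitoring Committee and later to readers. Events unrelated to PCI that occur equally in both arms also push a stroke ratio towards 1.

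The definition affects event handling too. Section 5.2 exempts its listed outcomes from separate SAE reporting, and section 9.1 sends unexpected events that are not defined outcomes down the adverse-event route. What sits in the Stroke row therefore helps decide how an event is reported.

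**Working it through.** **1. Is list membership the definition?** Three rows of section 5.2 can be compared.

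- Hospitalisation first defines the event (an admission of at least 24 hours) and then classifies it.
- Atrial fibrillation first defines new onset and then classifies it.
- Stroke has no such first step. The event is whatever falls into one of the listed classes.

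The Hospitalisation row also sits badly with the Stroke row. It places stroke under cardiovascular causes, and mental deterioration of non-cerebrovascular origin under non-cardiovascular causes. A delirium admission could thus be a Stroke in one row and non-cardiovascular in another.

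**2. How many true strokes are expected?** The plan states no figure for stroke alone, so there is none to reproduce. The inputs are 350 participants allocated 1:1 (sections 5.1 and 16.1), hence 350 / 2 = 175 per arm, and 0.3% for procedural MI and stroke together.

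- PCI arm: 175 × 0.003 = 0.525. This is an upper bound for procedural stroke, because MI is included.
- Chance of at least one such event: 1 − 0.997^175 = 41%.
- Applied to all 350, which is generous because the figure is for PCI: 350 × 0.003 = 1.05.

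One misfiled event in the PCI arm is 1 / 175 = 0.57%, already above the 0.3%. These figures leave out strokes after the procedure and up to six months, for which the document gives no rate.

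**3. What share of counted events could be non-strokes?** Let *d* be the rate of counted events that are not strokes and *s* the true stroke rate, over all 350. The share is d / (d + s). Every *d* is an assumption, because the document gives no delirium or TIA rate. For *s*, 0.3% is the figure above and 1% is an assumed six-month rate.

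| d (assumed) | Events, 350 × d | Share if s = 0.3% | Share if s = 1% |
|---|---|---|---|
| 0.1% | 0.35 | 25% | 9% |
| 0.3% | 1.05 | 50% | 23% |
| 1% | 3.5 | 77% | 50% |
| 2% | 7 | 87% | 67% |
| 5% | 17.5 | 94% | 83% |

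Non-strokes outnumber strokes only where *d* exceeds *s*.

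**4. Effect on a between-arm comparison.** If *d* is equal in both arms, the ratio becomes (p1 + d) / (p0 + d), while the difference p1 − p0 is unchanged in expectation. As an illustration on assumed values, take p1 = 0.6%, p0 = 0.3% and d = 1%. The ratio falls from 2 to 1.6 / 1.3 = 1.23, and the difference stays at 0.3 percentage points.

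**The case against.** **It may be only a classification scheme.** Section 5.2 reproduces consensus schemes whole. The Bleeding row includes a class for no bleeding, and the Repeat revascularisation row lists target lesion and target vessel, which are not events. The Stroke row may likewise be meant for coding, with subtypes separable later. This is plausible, but the row does not say it. The no-bleeding class excludes itself by name, and Type 3b does not.

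**Recovery-room confusion may not qualify.** A reader might infer that any participant who is confused after sedation becomes a stroke, and that such cases would swamp the true strokes. The document does not support this. The table is introduced as serious adverse events, section 9.2 ties seriousness to outcomes such as death, hospitalisation or its prolongation, and disability, and section 6.5.5 treats recovery from sedation as routine observation. Brief confusion may therefore stay out, although Type 3b itself sets no seriousness threshold. The swamping claim also needs a delirium or TIA rate that the document does not give.

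**The SAP could settle it.** Which subtypes enter a summary count is often left to the SAP. Here, however, section 5.2 fixes the definition, and an SAP that counted only Type 1 would depart from it.

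**The harm to inference is small.** This stands. Stroke is not the primary or a key secondary outcome and is not in the win-ratio hierarchy. Sedation precedes randomisation, so its effects should balance between arms. With about one expected event there is little comparison to dilute. Type 2 adds little, because the trial schedule in section 6.12 has no neuroimaging and covert lesions would surface only by chance.

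**Conclusion.** The defect in wording is real: as written, the Stroke outcome includes covert CNS injury, TIA and delirium without CNS injury. The expected number of true procedural strokes is small, at most about 0.5 in 175 PCI patients on the protocol's own combined figure, so a few misfiled events could materially inflate the reported rate and weaken a relative comparison.

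The size of the inflation cannot be fixed from the document. The share of counted events that are not strokes runs from about 9% to 94%, for assumed non-stroke rates of 0.1% to 5% and true stroke rates of 0.3% or 1%. It is not established that non-strokes would be the majority, or that ordinary post-sedation confusion would be counted. The primary and key secondary results, the sample size and the power are unaffected.

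**What to change.** In section 5.2, state that the outcome Stroke counts only overt CNS injury (NeuroARC Type 1). List covert injury (Type 2), TIA (Type 3a) and delirium without CNS injury (Type 3b) as separately named neurological outcomes that do not count as stroke. Keep them within section 5.2, so that their reporting route does not change by accident, and keep recording the NeuroARC type for each event.

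The cost is a short change of text and one derived variable. The stroke count becomes smaller, and nothing extra is collected.
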